#### 12.4.5 Safety variables

The safety variables will be analyzed for the SES by using descriptive summary statistics, frequency tables, and shift tables where appropriate.

AEs will be coded according to the MedDRA version that is in effect when the study is initiated. Only TEAEs will be analyzed, which are defined as AEs with onset or worsening after the first administration of IP up to and including the end-of-study visit (V18 [Week 64]) or, for subjects leaving the study prematurely, up to last recorded contact with the subject within 64 weeks after first injection. Incidences will be calculated for TEAEs at the system organ class level and at the preferred term level and will be presented by treatment, by injection cycle and overall. Additionally, TEAEs will be analyzed by worst intensity and by outcome. Listings and, if appropriate, tables displaying incidences for TEAEs leading to discontinuation, serious TEAEs, TEAEs of special interest, and deaths will also be provided.

Laboratory evaluations and vital signs (values and changes from baseline) will be analyzed descriptively by treatment and screened for individual notable values and/or changes.

The number of subjects with suicidal ideation, suicidal behavior, and self-injurious behavior without suicidal intent during treatment based on the C-SSRS will be calculated and presented as proposed in the Columbia–Suicide Severity Rating Scale Scoring and Data Analysis Guide Version 2.0 (Finalized February 2013) [Mary E. Nilsson 2013], Table 1.

In addition, for all subjects the electronic text-string search as described in the article by Posner at al. [Posner 2007b], section "Pharmaceutical company identification of possibly suicidal events" will be used to identify adverse events that could represent "possibly suicidal" events. Findings will be listed.

All analyses will be performed by age groups and treatment and additionally for the group of subjects of all ages (2-17) who received NT 201 in the respective treatment period (main or extension period).

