#### Columbia-Suicide Severity Rating Scale (C-SSRS)

Prospective monitoring of suicidality with the Columbia-Suicide Severity Rating Scale (C-SSRS) should be considered the most important (but not the only) source of information concerning suicidality.

Suicidality is assessed prospectively in subjects at baseline and every scheduled and unscheduled post-baseline site visit. The appropriate version of this scale ensures the consistent application of this important measure regardless of indication or investigator experience with the subject matter. With C-SSRS in place, administration of this semi-structured clinician-based assessment scale is standardized. The C-SSRS quickly and efficiently identifies those subjects that require additional clinician follow up.

Following versions of the C-SSRS are to be applied only for newly recruited subjects:

- 1. Children's baseline / screening version
- 2. Children's since last visit version.

The C-SSRS interview should only be assessed with children of respective age and cognitive state. Clear age cut-offs for the C-SSRS were not defined by the authors, but it has been found that administration is possible in general for children with a developmental age of about 7 years. Otherwise it should be documented in the electronic Case Report Form (eCRF) that a child was not able to assess the C-SSRS at a respective visit.

At the end of the assessment the subject should not be released from the study center until the results of the C-SSRS (positive or negative) are reviewed and the subject is not considered to be at risk. If there is doubt about whether a subject is at risk, the investigator should obtain appropriate psychiatric consultation.

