Eyelid function disorder	Respiratory failure	
Eyelid ptosis	Speech disorder	
Facial paralysis	Trigeminal nerve paresis	
Facial paresis	Urinary retention	
Hemiparesis	Vision blurred	
Hypoglossal nerve paresis	Vocal cord paralysis	
Hyporeflexia	Vocal cord paresis	
Hypotonia		
Wording of preferred terms is according to MedDRA version 22.0		

Table 4: List of Adverse	Events of Special	Interest Possibly I	ndicating Toxin Spread
Table 4. List of Auverse	Events of Special.	Interest I ussibly II	nuicating Toxin Spicau

To fulfill FDA requirements, TEAE data will be screened for suicidal events. The MedDRA Preferred Terms of all TEAEs will be checked using standard MedDRA query (SMQ) 'Suicide/self-injury'. Resulting TEAE findings will be listed in a separate listing. A list of the MedDRA Preferred Terms of the SMQ 'Suicide/self-injury' based on MedDRA version 22.0 is given in Table 5 (version in effect at database closure).

MedDRA Preferred Term:	MedDRA Preferred Term:	
Assisted suicide	Self-injurious ideation	
Columbia suicide severity rating scale abnormal	Suicidal behaviour	
Completed suicide	Suicidal ideation	
Depression suicidal	Suicide attempt	
Intentional overdose	Suicide threat	
Intentional self-injury	Suspected suicide	
Poisoning deliberate	Suspected suicide attempt	
Wording of preferred terms is according to MedDRA version 22.0		

In addition all comment fields of the case report form (CRF) and all investigator reported terms of TEAEs will be screened for the following terms or term elements ('strings') and listed in a separate listing:

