#### Table 6: List of Search Terms and Search Strings of Possibly Suicidal Events

Term:	Term:
attempt	self inflict
cut	self injur
gas	self-damage
hang	self-harm
hung	self-inflict
jump	self-injur
mutilate	shoot
overdos	slash
self damage	suic
self harm	

Obvious false positive findings will be excluded from the listing (e.g., 'gas' in 'gastrointestinal' or 'cut' in 'acute' or in 'cutaneous').

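### The SAP Table 6 string search cannot find '-mutilation', '-mutilating', '-damaging' or poisoning wording, which leaves a small gap in CRF comment fields and in reported terms coded outside Table 5

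*SAP*

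**What the plan says.** SAP Section 7.5, under Adverse Events, plans two screens that run side by side.

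- **Coded terms.** "The MedDRA Preferred Terms of all TEAEs will be checked using standard MedDRA query (SMQ) 'Suicide/self-injury". The SMQ terms are in Table 5. They include "Poisoning deliberate" and 'Intentional self-injury'.
- **Free text.** In addition, "all comment fields of the case report form (CRF) and all investigator reported terms of TEAEs will be screened for the following terms". The SAP describes what is searched for as "terms or term elements ('strings') and listed in a separate listing". The 19 strings are in Table 6, titled "List of Search Terms and Search Strings of Possibly Suicidal Events".

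The note below Table 6 says that obvious false positives are removed and gives as examples "gas' in 'gastrointestinal' or 'cut' in 'acute' or in 'cutaneous".

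Protocol Section 12.4.5 is the origin of the free-text screen: "In addition, for all subjects the electronic text-string search as described in the article" it cites. It says that the findings will be listed.

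**The concern.** Table 6 is inconsistent in how it forms its strings. Some entries are cut so that they catch every ending of a word: 'overdos' finds overdose and overdosing, and 'suic' finds suicide and suicidal. Three entries keep their final 'e': 'mutilate', 'self damage' and 'self-damage'. They therefore fail on the -ion and -ing forms, including 'self-mutilation', which is the ordinary noun for the behavior. Poisoning has no string at all, although the SAP's other list treats deliberate poisoning as a suicide or self-injury term.

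What is at stake is how the listing is read. A listing with no such entries would be taken to mean that the text was searched and nothing was found, when the search could not have found these words.

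**Working it through.** No sample size, power or error rate is involved, and the plan states no figure to reproduce. The check is a string comparison.

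**Inputs.** The 19 strings of SAP Table 6, the 14 preferred terms of SAP Table 5, and a set of ordinary test entries.

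**Step 1: how strings are matched.** The false-positive examples ('gas' in 'gastrointestinal', 'cut' in 'acute') can arise only if a string is matched inside a longer word. The rule is therefore: an entry is found if at least one Table 6 string occurs as an unbroken run within it. I assumed that upper and lower case are treated alike, which the SAP does not state.

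**Step 2: the three full words.** 'Mutilate' and 'mutilation' share 'mutilat' and then differ ('e' against 'i'), so the first is not contained in the second. The same holds for 'self-damage' and 'self-damaging' after 'self-damag'.

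**Step 3: test entries, Table 6 as written and with the four changes given below under the fix.**

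| Entry | As written | Changed |
|---|---|---|
| self-mutilation, self mutilation | no match | 'mutilat' |
| self-mutilating behaviour | no match | 'mutilat' |
| mutilated, mutilates | 'mutilate' | 'mutilat' |
| self-damaging behaviour | no match | 'self-damag' |
| self damaging | no match | 'self damag' |
| self-damage, self-damaged | 'self-damage' | 'self-damag' |
| deliberate poisoning, intentional poisoning | no match | 'poison' |
| self-poisoning, poisoned himself | no match | 'poison' |
| self-inflicted poisoning | 'self-inflict' | 'self-inflict', 'poison' |
| gas poisoning | 'gas' | 'gas', 'poison' |

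A poisoning entry is found at present only when it also contains another listed string.

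**Step 4: the two lists side by side.** Of the 14 Table 5 terms, 13 contain a Table 6 string. The exception is 'Poisoning deliberate'. With 'poison' added, 14 of 14 do. This compares the two lists and does not measure a loss: a TEAE coded to any Table 5 term is listed through the SMQ check, so the two screens together already cover 14 of 14.

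**Step 5: where a missed entry has no second screen.**

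- CRF comment fields: the SMQ check works on coded TEAE terms and does not reach them, so the string search is the only planned screen of that text.
- Reported TEAE terms coded to a preferred term outside Table 5: the SMQ check does not list them. The documents do not show how 'self-mutilation' would be coded, so it cannot be said on which side it falls.

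**The case against.** The strongest objection is that the protocol fixes this search by reference to a published article. If Table 6 reproduces that article's list, the SAP does what the protocol asks, and editing the strings is a preference for a better list. The article is not available here, so this cannot be settled, and no departure from it is claimed. The objection does not stand against the remedy, however. Each shorter stem finds everything that the full word finds, and 'poison' is an addition, so the search is only widened.

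A second objection is that the SMQ check catches the important cases, and that Protocol Section 10.1 requires adverse events to be sought at each visit and recorded. This stands in large part and is why the gap is narrow. It does not cover text that appears only in a comment field.

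Two stronger readings are tempting.

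- A reader might infer that the string search is the main systematic check for children who cannot be interviewed, because the C-SSRS section says that "administration is possible in general for children with a developmental age of about 7 years". The documents do not support this. The same section says that no clear age cut-offs were defined. Protocol Section 10.7 provides for questions to parents or caregivers as well as subjects. The SMQ check covers the TEAEs of all subjects, and Protocol Section 7.4 makes suicidality risk, in the investigator's judgment, a criterion before each re-injection.
- A reader might also connect the gap with withdrawal, because Protocol Section 7.5.1 names non-suicidal self-injurious behavior as a reason. That decision is made by the investigator during the study. The string search feeds a listing in the single final analysis (SAP Section 3.1) and can neither cause nor prevent a withdrawal.

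**Conclusion.** The point holds as a minor defect of the string search. As written, Table 6 cannot find the -ion and -ing forms of mutilate, the -ing form of self-damage, or poisoning wording that carries no other listed string. The consequence is limited to CRF comment fields and to reported terms coded outside Table 5, and to one safety listing. No efficacy result, incidence table or error rate is affected.

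The number of records concerned is unknown from the documents and probably small. The conclusion rests on matching inside words, which the SAP's own examples imply, and on matching that ignores case, which is assumed.

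**What to change.** In SAP Table 6:

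- replace 'mutilate' by 'mutilat';
- replace 'self damage' by 'self damag' and 'self-damage' by 'self-damag';
- add 'poison'.

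Keep the other strings and the manual removal of obvious false positives. A short note should say that these strings were widened or added, so that the relation to the cited article stays clear.

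The cost is three edited strings and one new string in one program, plus a few more false positives to remove by hand, for example accidental or food poisoning. The change does not make the list complete: closed-up spellings such as 'selfharm' and 'selfinjury' match neither the present nor the changed strings.

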#### Table 6: List of Search Terms and Search Strings of Possibly Suicidal Events

Term:	Term:
attempt	self inflict
cut	self injur
gas	self-damage
hang	self-harm
hung	self-inflict
jump	self-injur
mutilate	shoot
overdos	slash
self damage	suic
self harm	

Obvious false positive findings will be excluded from the listing (e.g., 'gas' in 'gastrointestinal' or 'cut' in 'acute' or in 'cutaneous').

#### Vital signs, body weight, and BMI

The individual blood pressure, heart rate, body temperature, body weight, height and BMI data will be listed. Vital signs, body height and weight and BMI will be summarized (n, mean, standard deviation, minimum, 1st quartile, median, 3rd quartile and maximum) at each time

point. Descriptive statistics will be given for absolute values and changes from baseline (V2) to all post-baseline visits.

Frequencies of subjects with lowered, normal, or raised values will be displayed as shift tables from baseline (V2) to all post-baseline visits.

High and low values are defined as given in **Table 7**.

Vital Sign Variable	Flag	Observed Value 
	High	≥ 180
Systolic Blood Pressure (mmHg)	Low	≤ 90
	High	≥ 105
Diastolic Blood Pressure (mmHg)	Low	≤ 55
	High	≥110
Heart rate (bpm)	Low	$\leq$ 50
	High	Not applicable
Height (cm)	Low	Not applicable
	High	Not applicable
Weight (kg)	Low	Not applicable
2	High	> 30.0
BMI (kg/m  )	Low	≤ 18.5
Temperature (°C)	High	> 37.5
	Low	< 36.5

## Table 7: High and Low Values of Vital Signs

 A value is considered as high/low if it meets the criterion for observed values

## Laboratory data

Descriptive summary statistics for original values and for the changes from study baseline will be displayed for each parameter.

Furthermore, the number of subjects with lowered, normal, or raised values compared to normal range will be displayed as shift tables from Screening to final visit of main period V6 and end-of-study visit V18. Laboratory parameters will be sorted by predefined categories (Hematology and clinical chemistry).

Unscheduled and doubly performed laboratory data will be listed individually. For additionally performed laboratory measurements of certain subjects on other visit dates or of other laboratory parameters than planned no shift tables or descriptive statistics will be created.

The first valid value will be analyzed for all post-baseline visits. In case no exact value is given ( $\langle x.x, \rangle x.x$ ) the respective higher/ lower value will be used, e.g.  $\geq$ 1.24 will be changed to 1.241 and <0.5 will be changed to 0.49.

#### Antibodies against BoNT-A

Occurrence of antibodies against BoNT-A in subjects with  $\geq 30$  kg BW will be analyzed descriptively (frequency tables by category and shift tables from baseline (V2) to end-of-study visit V18) and screened for individual notable values and/or changes. In case blood sample is taken at V17 instead of V18 these values are used for analyses.

#### C-SSRS

The number of subjects with suicidal ideation, suicidal behavior, and self-injurious behavior without suicidal intent during treatment based on the C-SSRS will be calculated and presented as proposed in the Columbia–Suicide Severity Rating Scale Scoring and Data Analysis Guide Version 2.0 (Finalized February 2013)[Mary E. Nilsson 2013].

Questions which were documented between one day after start of MP and up to start of OLEX will be assigned to MP. For subjects who discontinued during MP, all questions which were documented at least one day after start of MP will be assigned to MP. Questions which were documented at least one day after start of OLEX will be assigned to OLEX.

The following outcomes are C-SSRS categories and have binary responses (yes/no).

Category 1 – Wish to be Dead

Category 2 – Non-specific Active Suicidal Thoughts

Category 3 – Active Suicidal Ideation with Any Methods (Not Plan) without Intent to Act

Category 4 – Active Suicidal Ideation with Some Intent to Act, without Specific Plan

Category 5 - Active Suicidal Ideation with Specific Plan and Intent

Category 6 – Preparatory Acts or Behavior

Category 7 – Aborted Attempt Category 8 – Interrupted Attempt Category 9 – Actual Attempt (non-fatal) Category 10 – Completed Suicide

The following composite endpoints will be calculated:

- 1. Suicidal ideation (MP): A "yes" answer during MP to any one of the five suicidal ideation questions (categories 1-5) on the C-SSRS.
- 2. Suicidal behavior (MP): A "yes" answer during MP to any one of the five suicidal behavior questions (categories 6-10) on the C-SSRS.
- 3. Suicidal ideation or behavior (MP): A "yes" answer during MP to any one of the ten suicidal ideation and behavior questions (categories 1-10) on the C-SSRS.
- 4. Suicidal ideation (OLEX): A "yes" answer during OLEX to any one of the five suicidal ideation questions (Categories 1-5) on the C-SSRS.
- 5. Suicidal behavior (OLEX): A "yes" answer during OLEX to any one of the five suicidal behavior questions (Categories 6-10) on the C-SSRS.
- 6. Suicidal ideation or behavior (OLEX): A "yes" answer during OLEX to any one of the ten suicidal ideation and behavior questions (Categories 1-10) on the C-SSRS.

Frequency tables for the composite endpoints and for the single questions for these time periods will be created. All subjects who filled out at least one questionnaire during the respective period will be used for the denominator whereby only questions which are referring to the time period since last visit are regarded. Furthermore, information on C-SSRS will be listed for subjects with at least one post-baseline suicide-finding during MP (including V6) and for subjects with at least one post-baseline suicide-finding after V6. In case the questionnaire was not filled out on a visit date the previous visit will be assigned in the listing.

# 7.6 Other Variables

#### Disposition, demographic and other baseline data

Subject dispositions, demographic data, and baseline characteristics (including height, weight and BMI at screening V1) will be presented using standard descriptive statistics; no homogeneity tests will be performed. Demographic data will be summarized for screening failures, the SES of MP (actual treatment will be displayed), the FAS (planned treatment will be displayed), the PPS and the SES of OLEX. The analyses of the MP will be stratified by "Placebo (6-17 years)", "NT 201 (6-17 years)", "NT 201 (2-5 years)" and "Total NT 201 (2-17 years)". For tables including all enrolled/randomized subjects, the additional "Total" column will be displayed. For the OLEX, two sets of tables will be produced: one "respective of main period treatment" showing "NT 201 (MP=Placebo, 6-17 years)", "NT 201 (MP=NT 201, 6-17 years)", "NT 201 (MP=NT 201, 2-5 years)", "NT 201 (MP=NT 201, 2-17 years)" and another set "irrespective of main period treatment" showing "NT 201 (6-17 years)", "NT 201 (2-5 years)" and "NT 201 (2-17 years)".

A table given the absolute and relative frequencies for the following European Union Drug Regulatoring Authorities Clinical Trials (EudraCT) age categories will be generated:

- 2-11 years
- 12-17 years.

Furthermore, the absolute and relative frequencies for the following age categories will be generated:

- 2-5 years
- 6-9 years
- 10-12 years
- 13-17 years.

The weight at baseline will be classified in the following categories:

- >= 12 kg and <15 kg
- >= 15 kg and < 19 kg
- >= 19 kg and <23 kg
- >= 23 kg and <27 kg
- >= 27 kg and <30 kg
- >= 30 kg.

A table giving the absolute and relative frequencies for subject's reason for premature study discontinuation will be generated giving all reasons as documented in the CRF. The analysis will be based on all randomized/ assigned subjects of MP and on all subjects entered OLEX for OLEX. The randomized/ assigned treatment group will be displayed. For the extension period the reason will be summarized overall and for each cycle. The following subjects are regarded as completers for MP:

- Subjects who are included in SES OLEX or
- Subjects who performed last visit at day 95 or later

Additionally, the reason will be summarized for the complete study for randomized/ assigned subjects. Further, for MP and OLEX, the main reason will be tabulated by using the following approach for identification: chose from the reasons that are documented for a subject that one that occurs first in the list as main reason. The list is as follows:

- 1. Death
- 2. Pregnancy
- 3. Adverse Event(s)
- 4. Lack of efficacy
- 5. Withdrawal by subject
- 6. Physician decision
- 7. Protocol deviation
- 8. Lost to follow-up
- 9. Other.

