#### Placebo-controlled main period (first injection cycle)

- Baseline injection visit [V2] (Day 1 of first injection cycle; randomization).
- Assessment visit [V3] (Week 4 ± 3 days).

- Assessment visit [V4] (Week 8 ± 7 days).
- Assessment visit [V5] (Week  $12 \pm 7$  days).
- Final visit of main period [V6] (Week 16 ± 2 weeks).

**Open-label extension period** (second, third and fourth injection cycle)

Second injection cycle ( $16 \pm 2$  weeks after 1st injection):

- Injection visit [V6a] (Day 1 of second injection cycle).
- Assessment visits [V7] (4 weeks ± 3 days after the 2nd injection) and [V8, V9] (8, 12 weeks ± 7 days after the 2nd injection).
- End of cycle visit [V10] (16 weeks ± 2 weeks after 2nd injection).

*Third injection cycle*  $(16 \pm 2 \text{ weeks after 2nd injection})$ :

- Injection visit [V10a] (Day 1 of third injection cycle).
- Assessment visits [V11] (4 weeks ± 3 days after 3rd injection) and [V12, V13] (8, 12 weeks ± 7 days after 3rd injection).
- End of cycle visit [V14] (16 weeks  $\pm$  2 weeks after 3rd injection).

Fourth injection cycle ( $16 \pm 2$  weeks after 3rd injection):

- Injection visit [V14a] (Day 1 of fourth injection cycle).
- Assessment visits [V15] (4 weeks ± 3 days after 4th injection) and V16, V17] ( 8, 12 weeks ± 7 days after 4th injection).
- End of cycle/study visit [V18] (16 weeks  $\pm$  2 weeks after 4th injection).

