# 7.4 Eligibility criteria for continued treatment in the extension period

Criteria for the transition to the extension period (V6/6a) and for continued treatment within the extension period (V10/10a and V14/14a) are listed below. (Note that the pairs of visits 6/6a, 10/10a and 14/14a will normally take place on the same respective day.)

If these eligibility criteria are not fulfilled at the end-of-cycle visit postponement of study treatment may take place at the beginning of the following injection cycle of the extension period. The re-injection visit can be postponed for up to a maximum of two weeks (but no longer than 18 weeks after the preceding treatment visit). For subjects who still do not fulfill the eligibility criteria at the revisit, study participation will be ended.

	Eligibility Criteria for Extension Treatment	Ratio- nale	Visits 6, 6a, 10, 10a, 14, 14a
1.	Clinical need for re-injection.	Ind	Х
2.	Absence of medically-relevant severe adverse events of special interest that are judged to have a causal relationship to the study treatment (indicative of toxin spread in the area of injection), especially respiratory arrest/distress/failure and dysphagia necessitating diet changes occurred during any period of the study.	Safety	Х
3.	No concomitant infection or inflammation in the head and neck region.	Safety	Х

Page 52 of 183

		Eligibility Criteria for Extension Treatment	Ratio- nale	Visits 6, 6a, 10, 10a, 14, 14a
4.	Neg fem	ative result of pregnancy test (testing only performed for ale with history of menarche, i.e. the first menstrual bleeding).	Safety	Х
5.	No :	significant risk of suicidality since last injection based on the Investigator's judgment, and	Safety	Х
	•	if appropriate, as indicated by a response of "no" to questions 4 or 5 in the suicidal ideation section of the C-SSRS		
	•	and no non suicidal self-injurious behavior		
	•	and no suicidal behavior.		

Definition of indication for continued study treatment [Ind]; administrative [Adm].

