Subjects who are withdrawn from the study because of AEs will be treated by standard clinical methods and will be followed up until (and including) the last scheduled visit of the injection cycle in which they were withdrawn or until 28 days after the onset of the adverse event, whichever date is the later. All pertinent information concerning the AE will be documented in the subject's hospital medical file as well as in the eCRF AE report form.

Following a subject's withdrawal, a final examination should be performed for safety reasons if parents/carers are willing to bring the child for the visit. The investigator is required to make every effort to contact subjects lost to follow-up, and all such efforts are to be documented in the subject's hospital medical file (e.g., times and dates of telephone contact, copies of letters).

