# **10** SAFETY ASSESSMENTS

### **10.1** Definition of an adverse event

An AE is any untoward medical occurrence in a subject administered a pharmaceutical product that does not necessarily have a causal relationship with the treatment. Thus, an AE can be any unfavorable and unintended sign, symptom, or disease (including intercurrent illness); deterioration of a pre-existing illness; accident; any suspected drug reaction; or a clinically relevant change of laboratory values whether or not considered related to the IP and/or study treatment.

Changes in efficacy variables (e.g., subject-reported outcome variables [questionnaires and scales] during the course of the study) need not be documented as AEs, because these changes will be recorded as efficacy variables. Elective treatments planned before screening and which are documented in the subject's source data are usually not regarded as AEs.

The period of observation for AEs extends from the time when the informed consent form was signed until the subject's final study visit. Any medical occurrence between the time when the informed consent form is signed and the first intake of study medication is an AE and has to be documented in the subject's file and in the eCRF AE report form.

Non-serious AEs will not be followed up after the final study visit (i.e.,  $16 \pm 2$  weeks after the last administration of NT 201), which will take place after a total of  $64 \pm 8$  weeks, at the end of the fourth injection cycle. In cases of study participation discontinuation the final visit takes place  $16 \pm 2$  weeks after the last administration of NT 201, after which no further visit for safety follow-up is considered necessary (see Section 9.2).

Pre-existing conditions that do not worsen during the course of the study are not reportable as AEs. To determine whether a condition has worsened, it is compared to the condition of the subject at screening. Abnormal clinically relevant laboratory values obtained during the subject's screening period will only meet AE criteria if newly detected.

Incidental findings of abnormal laboratory values will be reported to the investigator immediately so that the subject can promptly be referred for treatment and care.

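### The SAP decides main-period completion from the last-visit date, so a child withdrawn early but followed to Week 16 as the protocol requires is counted as a completer

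*SAP*

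**What the plan says.** SAP 7.6, under disposition, specifies a table of reasons for premature discontinuation. On its base it says: "The analysis will be based on all randomized/ assigned subjects of MP and on all subjects entered OLEX for OLEX". The same paragraph then gives the completer rule: "The following subjects are regarded as completers for MP", followed by two alternatives, "Subjects who are included in SES OLEX or" "Subjects who performed last visit at day 95 or later". The second alternative has no condition on whether, when or why the child was withdrawn.

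The protocol says when withdrawn children are last seen:

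- Section 7.5.1: children withdrawn because of AEs "will be followed up until (and including) the last scheduled visit of the injection cycle in which they were withdrawn", or until 28 days after AE onset if that is later. In the main period the last scheduled visit is V6.
- Section 10.1: "In cases of study participation discontinuation the final visit takes place" 16 ± 2 weeks after the last administration.
- Section 6.1.2: all who leave early are asked to attend the end-of-study examination.

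Section 7.5.1 also requires the withdrawal and its reason to be entered in the eCRF, and asks for the date and circumstances.

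**The concern.** A late last visit does not separate a child who completed the main period from one who was withdrawn and then followed for safety. The better a site follows Section 7.5.1, the more of its AE withdrawals the SAP labels as completers.

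A mislabelled child has not entered OLEX either, so is outside the base of the OLEX table. The withdrawal can then appear in neither period summary. The main period is the only randomized, placebo-controlled part of the trial, so its by-arm disposition table is where a reader looks for differential withdrawal. The loss is also selective. AE withdrawals carry the explicit follow-up duty, while children who leave without a late visit stay visible as non-completers.

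**Working it through.** The SAP gives no derivation of day 95, so there is no plan figure to reproduce. The check is date arithmetic.

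**Inputs.** Injection is Day 1 (Protocol 6.1.2). V5 is Week 12 ± 7 days and V6 is Week 16 ± 2 weeks (Protocol 6.1.2). AE withdrawals are followed to the later of V6 and AE onset + 28 days (Protocol 7.5.1). The cut-off is day 95 (SAP 7.6).

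**Where the cut-off lies** (study day = days since injection + 1)
- V5: 84 ± 7 = 77 to 91 days after injection, study days 78 to 92.
- V6: 112 ± 14 = 98 to 126 days after injection, study days 99 to 127.
- Day 95 lies in the gap between them. In effect the rule asks whether the child's last visit was a Week 16-type visit.

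**Last follow-up day of an AE withdrawal** = max(V6 day, onset + 28)

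| AE onset (study day) | Onset + 28 | Last follow-up (study day) | SAP label |
|---|---|---|---|
| 5 | 33 | 99 to 127 | completer |
| 30 | 58 | 99 to 127 | completer |
| 60 | 88 | 99 to 127 | completer |
| 95 | 123 | 123 to 127 | completer |
| 110 | 138 | 138 | completer |

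Every AE withdrawal followed as Section 7.5.1 requires passes the cut-off. A final visit timed as in Section 10.1 falls on days 99 to 127, with the same result for other discontinuations. (Section 10.1 refers to the last administration of NT 201; for a placebo child I read this as the last study injection.)

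**Possible size.** The documents give no main-period withdrawal rate, so both inputs here are assumptions: *w*, the true withdrawal proportion among the 219 randomized children, and *s*, the share of withdrawals with a last visit on day 95 or later.
- Mislabelled children = 219 × w × s
- Displayed completion = 1 − w(1 − s)

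| w | Withdrawals (219w) | Mislabelled, s = 25% to 100% | Displayed completion | True completion |
|---|---|---|---|---|
| 2% | 4.4 | 1.1 to 4.4 | 98.5% to 100% | 98% |
| 5% | 11.0 | 2.7 to 11.0 | 96.25% to 100% | 95% |
| 10% | 21.9 | 5.5 to 21.9 | 92.5% to 100% | 90% |

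**Contrast within the SAP.** For efficacy at Week 16 of cycle 4, SAP 7.1 includes only children who complete that cycle regularly. The main period has no such condition.

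**The case against.** Much of the opposing case stands, and it limits the point.

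- **Tolerability data are not lost.** A reader might infer that NT 201 would look better tolerated because AE withdrawals vanish. The documents do not support that. Treatment-emergent AEs leading to discontinuation are a secondary safety variable (SAP 6.5.2), tabulated by treatment, injection cycle and period (SAP 7.5). They come from a field on the AE record (Protocol 10.1), which is independent of the completer rule. SAP 7.6 also summarises reasons over the whole study.
- **Not every withdrawal is mislabelled.** Under Section 7.5.1 the final examination depends on the family's willingness, and Section 9.2 allows an unscheduled final assessment. A child last seen before day 95 is still a non-completer.
- **Failing re-injection eligibility is not a main-period withdrawal.** Protocol 7.4 says: "For subjects who still do not fulfill the eligibility criteria at the revisit, study participation will be ended". These criteria govern entry to the extension. A child who attends V6 and then fails them has completed the main period, and the SAP rule classes that child correctly.
- **Day 95 itself is not an error.** It precedes the earliest V6 (day 99) but follows the latest V5 (day 92), so it works as a tolerance for an early V6.
- **Removal from the table is inferred.** The SAP does not state that a completer's documented reason is dropped. The rule stands in the paragraph that defines the table, which makes this the natural reading, but the table layouts are in a separate appendix.

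It can also be argued that the main period has a single injection, so a child observed to Week 16 has finished its treatment and follow-up. That is a reason to report such children separately. It does not justify merging them with children who were never withdrawn.

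**Conclusion.** The point holds as a disposition-reporting error. Applied as written with Protocol 7.5.1 and 10.1, the SAP rule labels a child withdrawn earlier in the main period and followed to Week 16 as a completer. That child can then be absent from both period summaries.

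The direction is known: main-period withdrawals are understated, mainly those for AEs. The size is not known. The range of about 1 to 22 of 219 rests entirely on the assumed rates, and the effect on the comparison between arms depends on how withdrawals split, for which the documents give no figure. Absence from the main-period reason table also assumes that the completer rule determines who is counted there.

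The completer rule is not used to define the full analysis set or the per protocol set, and it does not enter the mixed model, so the co-primary results do not change.

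**What to change.** In SAP 7.6, keep the first completer condition. For children not in the OLEX safety set, require both a last visit on day 95 or later and no premature withdrawal documented in the eCRF with a date before the V6 visit. Count children withdrawn earlier but followed to Week 16 as main-period discontinuations, with their reason.

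Keep children who complete V6 and then fail re-injection eligibility or decline OLEX as main-period completers. Show them in a separate row, 'completed main period, did not enter OLEX', with reasons by randomized arm, so that no exit falls between the two period tables. The SAP should also say how an incomplete withdrawal date is handled.

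The cost is some SAP wording, one programming rule and one table row. The protocol already asks for the date and reason, so no new data are needed. The displayed main-period completion rate may be slightly lower.
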